- 3. The number of extra detected polyps by artificial intelligence with the histological diagnosis as a gold standard.
- 4. The endoscopist's polyp miss rate defined as the additional detection of polyps during colonoscopy
- 5. The false positive rate during clean withdrawal.

Exploratory endpoints

- 1. Correlation between the Boston Bowel Preparation Score and the number of false positive detections during colonoscopy.
- 2. Correlation between the endoscopist's historical adenoma detection rate and the number of extra detections and false negative detections by the artificial intelligence system.
- 3. Correlation between the polyp size and number of false negatives and additional detections.
- 4. Correlation between the Paris classification and the number of false negatives and additional detections.

- 5. Correlation between the total number of polyps per colonoscopy and additional detections.
- 6. Correlation between the experience of the endoscopist and additional detections.

6. Study Design

This is an investigator-initiated multicentre non-randomized prospective interventional trial to validate the performance of a novel state-of-the-art computer-aided diagnostic (CAD) tool in polyp detection implemented as second observer during routine diagnostic colonoscopy and to evaluate its feasibility in daily endoscopy. Consecutive patients referred for a screening, surveillance or diagnostic colonoscopy will be included. After standard bowel preparation with PEG based solutions, patients will undergo a standard colonoscopy performed by an endoscopist with moderate to high adenoma detection rate (ADR > 20% and < 50%). A second observer, who is not a trained endoscopist, but a person trained for recognition of polyps and endoscopic lesions (see section 8), will follow the procedure on a bedside AI-tool to count the number of detections made by the AI system and categorize the results into positive or negative results as follows (1) true positive, (2) false negative or (3) false positive (detailed description, see section 4).

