Exclusion criteria for study analysis

- Colonic inflammation of > 30cm during colonoscopy
- Incomplete colonoscopy for any reason
- Incomplete recording or technical failure of the artificial intelligence system

8. Study Procedures

Bowel preparation

Before endoscopy patients will be prepared either at home either in hospital with standard bowel preparation according to local practice in the respective research centers, with an oral polyethylene glycol based regimen and if necessary, with an additional water enema. During endoscopy, all residual stools will be removed from the colonic wall by rinsing with water with or without dimeticon. Every subject's bowel preparation will be scored using the Boston Bowel Preparation Scale (BBPS).

Endoscopy, video recording

Endoscopy will be performed in patients on the scheduled appointment as initially made after selection based on referral. Video recording of the procedure will be initiated to record the patient's number upon the case report form before the endoscope is introduced in the anal canal. Before withdrawal, a picture of the caecum needs to be taken. During withdrawal the bowel should be as maximal inflated as possible for a high-quality inspection. A single pass withdrawal will be applied during inspection.

If a polyp is found, it can be resected after an endoscopist's optical assessment. This endoscopist's optical assessment should include description of the polyp size, location, Paris classification and if possible endoscopic diagnosis of most probable histology (hyperplastic, sessile serrated, adenoma or carcinoma).

If more than 5 polyps with apparent hyperplastic morphology are found in the rectosigmoid, the first 5 polyps will be included for analysis of the AI tool performance and will be resected for histological assessment and inclusion in the study. Any additional apparent hyperplastic polyps in the rectosigmoid exceeding the number of 5 will be discarded from the study for practical reasons. Most of these polyps will be hyperplastic and are clinically irrelevant. Additional separate biopsies of these sometimes many polyps will incur unnecessary costs. The entire procedure needs to be recorded as one video.

Second observer

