As polyps are clustered within patients, we need to take into account a clustering effect. Based on pilot data the intraclass correlation (ICC) was estimated as 0.003 which can be considered as negligible. (This means that there are no patient-effects, which would mean that probabilities of detection differ between patients).

The sample size calculations below are performed for the number of polyps needed, assuming independence.

- A sample size calculation was performed for a McNemar test for paired proportions.
- Sensitivity is assumed to be >90% (pilot data)
- Power = 90%
- A 5% two-sided significance level a difference in accuracy between AI and endoscopist, assuming respectively 97% and 95% of accuracy
- Indicating a total number of 2084 polyps is needed to prove superiority.

Statistical analyses will be performed according to the accuracy and extra detections. Descriptive statistics will be used for continuous variables and expressed as mean, median and range values. Association BBPS, ADR and location will be examined through logistic regression method, ROC curves, sensitivity and specificity.

11. Informed Consent

Written consent documents will embody the elements of informed consent as described in the Declaration of Helsinki and the ICH Guidelines for GCP and will be in accordance with all applicable laws and regulations. The informed consent form describes the planned and permitted uses, transfers, and disclosures of the subject's personal and personal health information for purposes of conducting the study. The informed consent form further explains the nature of the study, its objectives, and potential risks and benefits, as well as the date informed consent is given. The informed consent form will detail the requirements of the participant and the fact that he or she is free to withdraw at any time without giving a reason and without prejudice to his or her further medical care.

The investigator is responsible for the preparation, content, and IRB or IEC approval of the informed consent form and if applicable, the subject authorization form. The informed consent form must be approved by both the IRB or IEC and the sponsor prior to use.

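### The location regression in section 10 omits polyp size and Paris class, so a location odds ratio may partly reflect polyp mix rather than location

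*Combined protocol and SAP*

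**What the plan says.** The only planned analysis of location is one sentence in section 10 (Statistical Consideration): "Association BBPS, ADR and location will be examined through logistic regression method, ROC curves, sensitivity and specificity". The sentence does not name the outcome, say whether the three variables enter together or singly, or list any adjustment variables. The nearest guide to the outcome comes shortly before it: "Statistical analyses will be performed according to the accuracy and extra detections".

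Section 8 (Endoscopy, video recording) requires several polyp features at one assessment, which is to contain "description of the polyp size, location, Paris classification and if possible endoscopic diagnosis of most probable histology (hyperplastic, sessile serrated, adenoma or carcinoma"). Size, location and Paris class carry no qualifier; endoscopic type is recorded only where possible.

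Section 5 uses two of these features, each by itself. Exploratory endpoint 3 is "Correlation between the polyp size and number of false negatives and additional detections" and exploratory endpoint 4 is "Correlation between the Paris classification and the number of false negatives and additional detections". Location is not among the primary, secondary or exploratory endpoints.

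Section 8 also has a rule that applies to one segment only. It begins "If more than 5 polyps with apparent hyperplastic morphology are found in the rectosigmoid" and continues, after keeping the first five, "Any additional apparent hyperplastic polyps in the rectosigmoid exceeding the number of 5 will be discarded from the study for practical reasons".

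**The concern.** An odds ratio for location estimated without polyp size or Paris class compares segments that may hold different kinds of polyp. If small or flat polyps are both harder to detect and more frequent in one segment, that segment will look worse even though detection does not depend on where the polyp lies.

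The two other variables named in section 10 cannot remove this. BBPS is scored for each subject and ADR is the endoscopist's historical rate, so within one colonoscopy neither distinguishes a small polyp from a large one, or a flat one from a pedunculated one. Separate correlations for size and Paris class do not help either, because they leave the location estimate unadjusted. The point therefore stands whether the section 10 regression is joint or one variable at a time.

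At stake is the interpretation of one exploratory result: a statement that the AI tool or the endoscopist performs differently in a given segment could be read as a property of the segment when it is a property of the polyps found there.

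**Working it through.** **The plan's own figure.** Section 10 gives no figure for the location analysis. The one it does give, 2084 polyps, belongs to the primary McNemar comparison. With accuracies of 97% and 95% and an assumption of independence (the discordant split is not stated), the discordant proportions are 0.97 × 0.05 = 0.0485 and 0.95 × 0.03 = 0.0285. The exact two-sided 5% test then has power 0.8995 at 2084, so the figure is reproduced. Adding covariates to the location model does not change it.

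**Expected events at the plan's rates.** AI misses: 0.03 × 2084 = 62.5, about 63. Endoscopist misses: 0.05 × 2084 = 104.2, about 104.

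**Can polyp mix alone produce a location effect?** Everything in this step except 2084, 5% and 3% is an assumption that the documents do not supply: 40% of polyps in the rectosigmoid (about 834 of 2084), two polyp types, one with higher odds of a miss, and no location effect within type. The miss rate in a segment is

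share of hard type × miss rate of hard type + share of easy type × miss rate of easy type.

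Worked example, 5% missed overall, hard type 80% of rectosigmoid and 50% of other polyps, miss odds ratio 3:
- Miss rates by type that give 5% overall: 6.64% (hard) and 2.32% (easy).
- Rectosigmoid: 0.8 × 6.64 + 0.2 × 2.32 = 5.8%. Elsewhere: 0.5 × 6.64 + 0.5 × 2.32 = 4.5%. Check: 0.4 × 5.78 + 0.6 × 4.48 = 5.0%.
- Crude odds ratio: (0.0578/0.9422) / (0.0448/0.9552) = 1.31.
- Standard error of the log odds ratio: √(1/48.2 + 1/785.4 + 1/56.0 + 1/1194.4) = 0.202. So z = 0.268/0.202 = 1.33, and the chance of p < 0.05 is about Φ(1.33 − 1.96) = 26%. Simulation with 600 trials gave 25%, and 4% once type was in the model.

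Range over the assumed inputs (simulation, with the normal approximation in brackets):

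| Overall misses | Hard type, rectosigmoid vs rest | Miss OR of hard type | Crude location OR | Significant at 5% |
|---|---|---|---|---|
| 5% | 70% vs 55% | 2 | 1.10 | 9% (7%) |
| 5% | 85% vs 45% | 4 | 1.53 | 57% (56%) |
| 3% | same two extremes | 2 to 4 | 1.10 to 1.52 | 7% to 36% (7% to 37%) |

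**A second set of assumptions.** Two equal groups of 1042 polyps, again with no location effect within type:

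| Detection, easy vs hard type | Hard share 60/40 | 70/30 | 80/20 |
|---|---|---|---|
| 97% vs 93% | OR 1.18, significant 13% | 1.40, 39% | 1.67, 71% |
| 98% vs 90% | 1.33, 34% | 1.79, 87% | 2.46, about 100% |

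For example, 97% vs 93% at 70/30 gives detection of 0.7 × 0.93 + 0.3 × 0.97 = 94.2% against 95.8%, and (0.958/0.042)/(0.942/0.058) = 1.40. The second row implies 6% missed overall, above the plan's 5%. With equal mix (50/50) the odds ratio is 1.00.

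These results show the mechanism and its sensitivity to the inputs. They are not estimates for this trial.

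**The case against.** The strongest reply is that section 10 is silent rather than wrong. It promises an association, not an independent effect, and a crude association is a legitimate target. Most of this stands.

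- **Where the tool adds detections is a marginal question.** A reader might infer that the crude by-segment result gives a biased answer to it. It does not: the crude result answers that question correctly. Adjustment answers a different one, whether location matters for polyps of the same size and shape.
- **The chain of confounding is incomplete.** A reader might infer that the documents demonstrate a spurious location effect. They do not. The rectosigmoid rule suggests a link between hyperplastic type and segment, but it is a handling rule with no distribution, and its cap removes surplus hyperplastic polyps from the analysed set. Nothing says that type affects detection. Conversely, size and Paris class are to be examined against detection, but nothing links them to segment.
- **The outcome is unnamed.** Specificity is mentioned and exploratory endpoint 1 pairs BBPS with false positives, so part of the sentence may concern false positives, for which polyp size and Paris class do not exist. The point applies only to polyp-level outcomes.
- **Consequences are limited.** No decision in the protocol turns on location. The further development described in sections 2 and 3 is of the characterisation tool, so an inference that detector training would be misdirected goes beyond the text.
- **The ROC curve.** It might seem that an ROC curve for a nominal variable must be dropped. The sentence may instead mean BBPS, ADR or the model's predicted probability, for which a curve is valid.
- **The return to about 5% false significance after adjustment holds by construction,** because the simulated type is binary, fully observed and free of error.

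What survives is narrower: the variable list, followed as written, leaves location unadjusted for features already recorded beside it and already regarded as worth testing against detection.

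**Conclusion.** The point holds in a limited form. The location odds ratio in section 10 would be unadjusted for polyp size and Paris class, and so could not support a statement that location itself affects detection. Whether bias arises depends on polyp features differing by segment and also bearing on detection; the documents suggest parts of this but establish neither its presence nor its size. Under the assumed mixes the crude odds ratio is about 1.1 to 1.5 in the first set and 1.2 to 2.5 in the second, with false significance from near the nominal 5% to near certainty at the most extreme setting. The primary comparison is paired within polyp and is not affected. Severity is low: an inexpensive improvement to an exploratory analysis.

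**What to change.** In section 10, replace the location part of the sentence with a short specification:

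1. Name two polyp-level outcomes: AI false negative, and additional detection by AI.
2. For each, report the crude association with location, labelled as descriptive.
3. Beside it, report a logistic model with location in few groups (for example rectosigmoid versus rest), polyp size, Paris class collapsed to few levels, BBPS and ADR, giving the location odds ratio with its 95% confidence interval.
4. Use Firth's penalised likelihood and keep the model small. With Paris class in two or three levels there are 5 or 6 coefficients, hence 63/5 = 12.6 or 63/6 = 10.5 expected AI misses per coefficient. Full multi-level Paris class and type would be too many. The roughly 104 expected endoscopist misses guide the additional-detection model.
5. Add endoscopic type only in a sensitivity analysis with a category for not recorded, since it is described only where possible.
6. Base any statement that location itself affects detection on the adjusted estimate.

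The cost is a few sentences of analysis text and a little code, with no new data, patients or procedures. The downside is a somewhat wider interval for location.

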Participating sites	 [name] - Nuovo Regina Margherita Hospital, Rome, Italy. [name] - University Hospitals Leuven, Leuven, Belgium. [name] - Krankenhaus Barmherzige Brüder, Regensburg, Germany [name] - Centre Hospitalier Universitaire de Nantes, Nantes, France [name] - Centrum Onkologii-Instytut im. Marii Skłodowskiej-Curie, Warschau, Poland [name] - Spire Portsmouth Hospital, Portsmouth, United Kingdom [name] - Universitäts Medizin, Mainz, Germany [name] – University Medical Center, Amsterdam, The Netherlands (with reserve) [name] – University Hospitals Ghent, Ghent, Belgium
Summary of major selection criteria	 ≥ 40 years Diagnostic or screening colonoscopy Ability to give informed consent by the patient or legal representative Any contraindication for colonoscopy or biopsies of the colon Therapeutic colonoscopy Uncontrolled coagulopathy Confirmed diagnosis of inflammatory bowel disease prior to the colonoscopy Short bowel or ileostomy

	 Lynch syndrome, FAP syndrome Pregnancy
Period of evaluation of a subject in the study	Procedural time of one colonoscopy
Version and date of final protocol	Version 1.8 – 26.05.2020
Version and date of protocol amendments	NA

2. Introduction

Colorectal cancer is the second most frequent cancer in the general population. Accurate detection of precursor lesions, namely adenomas, is crucial for prevention of cancer related mortality. The detection and certainly the characterisation (i.e. differentiation between benign and malignant polyps) can be challenging with highly variable detection rates between different operators resulting in different rates of interval cancers.¹ Despite the increasing quality of endoscopy equipment, the miss rate for polyps has been reported to be as high as 21%.² The possible explanations for this high miss rate are multifactorial, but at least to a large extent operator dependent.

Over the past years, deep learning has revolutionized the field of computer-aided analysis and has also entered the medical world with results matching or even surpassing human-expert-level performance.³

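### ADR has one value per endoscopist, but section 10 analyses it by logistic regression with no stated allowance for endoscopist, so its standard errors will be too small if endoscopists differ for other reasons

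*Combined protocol and SAP*

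**What the plan says.** Section 5 lists two exploratory endpoints that depend on a characteristic of the operator. Endpoint 2 is "Correlation between the endoscopist's historical adenoma detection rate and the number of extra detections and false negative detections by the artificial intelligence system". Endpoint 6 is "Correlation between the experience of the endoscopist and additional detections".

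The only analysis text for such associations is one sentence in section 10: "Association BBPS, ADR and location will be examined through logistic regression method, ROC curves, sensitivity and specificity". It covers ADR together with BBPS and location. It does not mention experience, and it does not say whether the records are polyps, procedures or endoscopists, or how the variance is obtained.

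Section 10 discusses clustering once, for the sample size: "As polyps are clustered within patients, we need to take into account a clustering effect". It continues: "Based on pilot data the intraclass correlation (ICC) was estimated as 0.003 which can be considered as negligible", and then "The sample size calculations below are performed for the number of polyps needed, assuming independence". Clustering by endoscopist or by site is not mentioned anywhere, although the Synopsis lists nine sites (one of them provisional). Section 8 (Baseline assessments, Demographics) records the performing endoscopist for every subject.

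**The concern.** BBPS and location vary among the patients and polyps of one endoscopist. Historical ADR does not, and experience is in effect fixed over the study. A slope on ADR is therefore estimated from differences between endoscopists, and its precision depends mainly on how many endoscopists there are.

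A logistic model on polyps or procedures with no endoscopist term assumes that, at a given ADR, all endoscopists share one probability. The question asked is narrower: is that probability related to ADR? If endoscopists of equal ADR differ for other reasons, such as technique, equipment or case mix, the model counts those differences as many independent observations and reports too small a standard error. Section 2 makes such differences plausible when it describes the causes of missed polyps as "at least to a large extent operator dependent".

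At stake is a statement about who benefits from the tool. A finding that endoscopists with a lower ADR gain more from AI would be quoted, and it could rest on chance differences among a few operators.

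**Working it through.** **1. The plan's own figure.** No figure is given for the ADR analysis. The 2084 polyps come from the McNemar calculation in section 10 (97% versus 95%, two-sided 5%, 90% power). The discordance is not stated. If the two calls are taken as independent, the discordant cells are 0.97 × 0.05 = 0.0485 and 0.95 × 0.03 = 0.0285, with sum 0.077 and difference 0.02.

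n = (1.96·√0.077 + 1.2816·√(0.077 − 0.02²))² / 0.02² = 2019, or 2069 with continuity correction (adding 1/0.02 = 50). Exact McNemar power at 2084 is 89.95%. The figure is sound, and nothing below changes it.

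**2. Inputs for the ADR check.**
- From the documents: 2084 polyps; extra-detection rate 5% (complement of the 95% endoscopist accuracy); ADR between 20% and 50% (section 6).
- Assumed, because the documents do not give them: 9, 18 or 30 endoscopists (9 is one per listed site); SD of the log-odds between endoscopists of 0.1, 0.25 or 0.5; ADR spread uniformly over its range; similar numbers of polyps per endoscopist; no true ADR effect.

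**3. Hand approximation.** With K endoscopists, m = 2084/K polyps each. The between-endoscopist ICC on the probability scale is about SD² × 0.05 × 0.95. The variance of the ADR slope is understated by the factor D = 1 + (m − 1) × ICC, so the false-positive rate of a nominal 5% test is 2 × [1 − Φ(1.96/√D)].

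Example: SD 0.5, K = 9. m = 231.6; ICC = 0.25 × 0.0475 = 0.0119; D = 1 + 230.6 × 0.0119 = 3.74; 1.96/√3.74 = 1.01; rate = 31%.

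**4. Results, for 9 / 18 / 30 endoscopists.**

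| SD | ICC | D | Rate, approximation | Rate, simulated polyp-level logistic test |
|---|---|---|---|---|
| 0.1 | 0.0005 | 1.11 / 1.05 / 1.03 | 6% / 6% / 5% | near 5% to 6% |
| 0.25 | 0.0030 | 1.68 / 1.34 / 1.20 | 13% / 9% / 7% | 14% / 9% / 7% |
| 0.5 | 0.0119 | 3.74 / 2.36 / 1.81 | 31% / 20% / 15% | 33% / 21% / 17% |

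Repeat simulations agree to about one percentage point (for example 32%, 22% and 16% at SD 0.5). With SD 0 the polyp-level test rejects about 5% of the time, so the excess comes from heterogeneity between endoscopists. Regressing one value per endoscopist on ADR, with t-based inference on K − 2 degrees of freedom, rejects about 4% to 6% in all these settings.

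For AI misses at 3% (complement of 97%), SD 0.5 gives 24%, 17% and 12%.

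**5. Does the stated ICC of 0.003 remove the problem?** It is a patient-level figure. If the same value held between endoscopists, it would match SD = √(0.003/0.0475) = 0.25, the middle row. With 2 polyps per patient, D = 1 + 1 × 0.003 = 1.003, which is indeed negligible. With 231.6 polyps per endoscopist, D = 1 + 230.6 × 0.003 = 1.69, which is not.

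**The case against.** Several counter-arguments have force.

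- **The plan does not prescribe a naive analysis.** Logistic regression could include a random intercept. This is fair: the polyp or procedure unit is the default reading of a sentence that groups ADR with BBPS and location, not stated text. But nothing in section 10 points the analyst towards an endoscopist term.
- **No test is planned.** The endpoints are exploratory, the associations are only to be examined, and the 5% level is attached to the primary comparison. That lowers the stakes. It does not remove the problem, because confidence intervals share the fault: a 14% false-positive rate means that a nominal 95% interval covers about 86% of the time.
- **Heterogeneity may be small.** Operators are restricted to a middle range of ADR. Polyps from one patient also share an endoscopist, so if the pilot included several endoscopists, 0.003 taken at face value would cap the between-endoscopist ICC and make SD 0.5 look high. The documents do not describe the pilot's operators. At SD 0.1 the inflation is trivial.
- **The introduction's remark concerns endoscopists' misses.** It does not show that AI misses vary by operator to the same degree, so the AI-miss figures are weaker than those for extra detections.
- **The remedy has limits.** In a deliberately extreme case, with volume rising 20-fold with ADR, the unweighted endoscopist-level regression rejected about 7% to 9% (proportions) or 6% to 12% (log-odds). The random-intercept alternative was not simulated.

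A reader might infer more than the documents support. One stronger reading is that the test would reject whenever endoscopists differ; the rates above show over-rejection, not certain rejection. Another is that logistic regression is planned for experience; section 10 does not name experience and gives no method for it. A third is that the primary result is compromised; this point does not touch it.

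**Conclusion.** The concern holds in limited form. Section 10 assigns a covariate that is constant within endoscopist to logistic regression, with no provision for differences between endoscopists, and leaves experience without a method. If the model is fitted to polyps or procedures without an endoscopist term, the ADR association will look more precise than it is.

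The size depends on two quantities that the documents do not give. For extra detections, and for 9 to 30 endoscopists, the nominal 5% error becomes about 7% to 14% at SD 0.25 and 17% to 33% at SD 0.5. It is close to nominal at SD 0.1. Few endoscopists with many polyps each is the worst case. The effect is confined to exploratory endpoints 2 and 6; the McNemar comparison and the 2084 polyps stand as far as this point goes. It is worth correcting because the conclusion at risk is practical and the correction is nearly free.

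**What to change.** Add to section 10:

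- The association of ADR with extra detections and with AI false negatives (exploratory endpoint 2) is analysed with the endoscopist as the unit: one proportion or log-odds per endoscopist, regressed on ADR with t-based inference. Alternatively, use a logistic model with a random intercept for endoscopist and small-sample degrees of freedom based on the number of endoscopists.
- Experience (exploratory endpoint 6) is analysed the same way, with its measure defined.
- The number of endoscopists is reported beside each of these results.
- Polyp-level or procedure-level models are kept for location and BBPS, which vary within an endoscopist.

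If volumes turn out to be very unequal and related to ADR, the unweighted regression should be checked against the random-intercept model.

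The cost is a few sentences. No new data are needed, since the performing endoscopist is already recorded. Intervals for ADR and experience will be wider, which reflects the real number of independent units.
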